6.1.1. Tables and Listings

Tables

In general, data will be summarized by cohort and all cohorts combined (cohort-total). Furthermore, selected cohorts may be combined (e.g. young and older cohorts). The cohorts and cohort-total will be presented in columns.

Descriptive summary tables as well as figures will be based on scheduled visits.

Continuous variables will be summarized by group using the following descriptive statistics: number of subjects with non-missing data (n), mean, standard deviation (SD), median, minimum (min) and maximum (max).

Descriptive statistics of titer and fold increase of titer will additionally include geometric mean and its two-sided 95% confidence interval (CI). The geometric mean titer (GMT) is calculated as the mean of the logarithm of the functional antibody titers, back-transformed into the original scale. Two-sided CIs will be obtained by calculating CIs using t-distribution for the mean of the logarithmically transformed assay results and transforming the limits back to the original scale.

Geometric mean fold rise (GMFR) is calculated as the mean of the difference of logarithmically transformed assay results (post vaccination time point – pre vaccination time point) and back-transformed into the original scale. Two-sided CIs will be obtained by calculating CIs using Student's t-distribution for the mean difference of the logarithmically transformed assay results and transforming the limits back to the original scale.

Categorical variables will be summarized by group presenting absolute and relative frequencies (n and %) of subjects in each category (including the category 'missing' if applicable). Percentages will be calculated based on the number of subjects in the respective analysis set (N) as denominator if not stated differently. Percentages may be presented with exact 95% Clopper-Pearson CIs.

SDs as well as CIs will only be calculated if values of at least 3 subjects are available.

Listings

Important Case Report Form (CRF) data as well as all relevant generated and transformed variables together with the original data items will be listed. Unless otherwise specified, cohort will always be included in listings, and listings will be sorted first by cohort, then by subject

number and finally, if applicable, by visit number and/or a relevant date (e.g. date of onset of Adverse Event (AE)).

Programming

SAS® (version 9.4 or higher) programming will be performed according to Staburo GmbH standards as defined in SOP001_PROGRAMMING [1] and related work instructions. Special attention will be paid to planning and performance of quality control measures as documented in the quality control plan for the analysis of this study (see also SOP002_PROGRAM_QC [2]).

Analysis Sets

The SCR will be used for disposition. The SAF will be used for analysis of safety and adverse events data. Some analyses of the adverse events will be repeated using the SAFB if the SAF and the SAFB sets differ. The IMM will be used for the analysis of immunogenicity data. The analyses may be repeated using the IMMPP if the two analysis sets differ significantly. This will be decided at the DRM.

If subjects by accident receive two different doses, they will switch the dose cohort and will be displayed for each immunization with the corresponding dose cohort. For combined analyses, subjects who received two different doses will be assigned to the lower dose.

Data of subjects who failed to complete all visits of the study (dropout or withdrawal) will be reported as far as their data is available.

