- b) Specific doses to be defined, but in the range given. Already given doses will not be repeated.
- c) De-escalation doses are discretionary and need not be administered in numeric order.

IM = Intramuscular; mRNA = messenger RNA; modRNA = nucleoside modified messenger RNA; RBD = receptor binding domain; S protein = SARS-CoV-2 spike protein.

Table 2: Summary of vaccine dose regimens for older adults aged 56 to 85 years in Part A

Vaccine / mRNA type	Vaccine encoded antigen	Vaccine IM	Part A - Cohort numbers & Dose (μg) (12 subjects per cohort) a									
		dosing regimen	8	9	10	11	12					
BNT162b3 / modRNA	Membrane- anchored RBD of the SARS-CoV-2 S protein	Prime: Day 1 Boost: Day 22	8F 3 μg b, d	9F 10 µg b, d	10F 20 µg b, d	11F 10 - 60 µg b, c	12F 10 - 60 µg b, c					

- a) All dose escalation doses used must be judged acceptable by the Safety Review Committee before use.
- b) Specific doses to be defined, but in the range given. Already given doses will not be repeated.
- c) A lower prime dose with higher boost dose posology may be used.
- d) SRC approved and already initiated cohorts.
- IM = intramuscular; mRNA = messenger RNA; modRNA = nucleoside modified messenger RNA; RBD = receptor binding domain; S protein = SARS-CoV-2 spike protein.

Note: The doses planned in this trial reflect emerging clinical data from the ongoing BNT162-01 and BNT162-02 trials with the related vaccine candidates BNT162b1 and BNT162b2 in younger adults (aged between 18 and 55 years) and older adults (adults aged between 56 and 85 years).

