# TRIAL-SPECIFIC ABBREVIATIONS/TERMS

Abbreviation/Term	Explanation
Allocated subject	Enrolled subjects who are allocated to IMP
BNT162a	BNT162 RNA-LNP vaccine utilizing uRNA
BNT162b	BNT162 RNA-LNP vaccine utilizing nucleoside modified mRNA (the variant BNT162b3 will be tested in this trial)
BNT162c	BNT162 RNA-LNP vaccine utilizing self-amplifying mRNA
CMI	Cell-Mediated Immunity
Cohort	In this document, the word cohort refers to groups of subjects receiving the same vaccine dose and belonging to the same age group (younger adults or older adult)
COVID-19	Coronavirus Disease 2019
CRP	C-reactive protein
Elderly	Adults aged 65 to 85 years
ELISA	Enzyme-Linked Immunosorbent Assay
ELISpot	Enzyme-Linked Immunosorbent Spot
Enrolled subjects	Subjects who signed an informed consent form, i.e., who gave informed consent
HLA	Human leukocyte antigen
IM	Intramuscular(ly)
IV	Intravenous(ly)
modRNA	Nucleoside modified mRNA
mRNA	Messenger RNA
Older adults	Adults aged 56 to 85 years
P/B	Prime/Boost: a dosing regimen, comprising a priming immunization and a boost immunization
PBMC	Peripheral blood mononuclear cell
PEI	(German) Paul-Ehrlich-Institut
RNA-LNP	RNA lipid nanoparticle
RNA-LPX	RNA lipoplex
saRNA	Self-amplifying mRNA
SARS	Severe Acute Respiratory Syndrome
SARS-CoV-2	The virus leading to COVID-19
uRNA	Non-modified uridine containing mRNA
VNT	Virus neutralization test
Younger adults	Adults aged 18 to 55 years

For standard abbreviations, see Section 10.9.

Page 24 of 133 Version: 10.0 Date: 12 MAY 2021

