#### 8.4 Treatment of overdose

Any dose of trial treatment above the planned dose specified in this protocol will be considered an overdose.

The sponsor does not recommend specific treatment for an overdose.

In the event of an overdose, the investigator should:

- Contact the sponsor's Medical Monitor immediately.
- Closely monitor the trial subject for any AE/SAE and laboratory abnormalities (at least for 7 d).
- Document the quantity of the excess dose as well as the duration of the overdose in the CRF.

Decisions regarding dose interruptions or modifications will be made by the investigator in consultation with the sponsor's Medical Monitor based on the clinical evaluation of the trial subject.

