5.1. Analysis Sets

Screened Set (SCR)

The screened set is defined as all subjects who signed informed consent.

Safety Set (SAF)

The safety set is defined as all subjects who received at least one dose of Investigational Medicinal Product (IMP).

Safety Boost Set (SAFB)

The safety boost set is defined as all subjects who received two doses of IMP (prime and boost immunization).

Immunogenicity set (IMM)

The immunogenicity set is defined as all subjects who received at least one dose of IMP and have at least one post-baseline functional antibody titer immunogenicity assessment.

Immunogenicity per-protocol set (IMMPP)

The immunogenicity per-protocol set is defined as all subjects included in the immunogenicity set that have no major protocol deviations as determined by the clinician.

Note: In all analysis sets, subjects will be assigned to the dose cohort according to the actual dose they received ("as treated").

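### In tables that span both immunizations, the SAP counts events after an accidental higher dose under the lower dose, and it does not define which analyses are combined

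*SAP*

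**What the plan says.** The rule is in SAP 6.1.1, in the paragraph on analysis sets. It opens with the trigger, "If subjects by accident receive two different doses", and continues that "they will switch the dose cohort and will be displayed for each immunization with the corresponding dose cohort". The next sentence reads: "For combined analyses, subjects who received two different doses will be assigned to the lower dose". No section says what a combined analysis is. It could mean pooled time intervals, pooled cohorts, or both.

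SAP 5.1 gives the general principle: "In all analysis sets, subjects will be assigned to the dose cohort according to the actual dose they received".

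For solicited reactions, SAP 6.4.1 and 6.4.2 define an interval after prime, an interval after boost, and the two together. For TEAEs, SAP 6.4.3 defines a prime interval, a boost interval, an interval from prime to 28 days after boost, and related TEAEs followed through Visit 10. SAP 6.7.2 tabulates laboratory shifts from baseline to the worst post-baseline value, which also spans both doses.

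Two protocol passages bear on the point. Section 8.4 states: "Any dose of trial treatment above the planned dose specified in this protocol will be considered an overdose". It also requires the excess quantity to be recorded in the CRF. Footnote c to Table 2, on older-adult Cohorts 11 and 12, says: "A lower prime dose with higher boost dose posology may be used".

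**The concern.** The trial describes tolerability by dose level. Suppose a subject is primed as planned and boosted by mistake with more. A severe reaction after that boost belongs to the higher dose. In any table covering the whole regimen, the SAP places it in the lower-dose column. The lower dose then looks less well tolerated than it was, and the higher-dose column lacks the event.

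For most outputs a boost-only table corrects this. One output has no such companion. A related TEAE starting more than 28 days after boost falls only in the interval through Visit 10. If that interval is a combined analysis, the summary tables show the event under the lower dose and nowhere else.

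For titers after boost, the SAP does not say which column a two-dose subject belongs in. A fold rise from baseline at those visits reflects both doses.

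**Working it through.** **Inputs.** Cohort size is 12 (Protocol 9.2, SAP 4). The assignment rule is from SAP 6.1.1 and the intervals from SAP 6.4.1 to 6.4.3. The number of misdosed subjects is not given, so one is assumed. Event rates per dose are also assumed, and the two doses are treated as independent.

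**The plan's own figure.** The probability of seeing a 15% event at least once in 12 subjects is 1 − 0.85^12 = 0.8578. This agrees with the stated 85.8%. It confirms the cohort size used below and is not in dispute.

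**Where an event after the higher dose is counted.**

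| Output | SAP | Column |
|---|---|---|
| Reactions to day 7 after prime, or after boost | 6.4.1, 6.4.2 | Dose given |
| TEAEs from prime to boost, or boost to day 28 | 6.4.3 | Dose given |
| Both reaction intervals together | 6.4.1, 6.4.2 | Lower dose |
| TEAEs from prime to 28 d after boost | 6.4.3 | Lower dose |
| Related TEAEs through Visit 10 | 6.4.3 | Lower dose, if a combined analysis |
| Laboratory shift to worst value | 6.7.2 | Lower dose, if a combined analysis |
| Titers and fold rise after boost | 6.5 | Not stated |
| Cohort-total | 6.1.1 | Unaffected |

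**Largest shift in the lower-dose column.** Let x of the 11 correctly dosed subjects have the event, and let the misdosed subject have it only after the higher dose. The shift is (x + 1)/12 − x/11.
- x = 0: 1/12 − 0/11 = 8.3 points
- x = 6: 7/12 − 6/11 = 3.8 points
- x = 11: 12/12 − 11/11 = 0

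Reaction tables use as denominator the subjects with diary data, so a column with fewer than 12 would move slightly more.

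**Expected shift.** Let pL and pH be the event rates after one lower and one higher dose. A correctly dosed lower-dose subject has an event over two doses with probability L = 1 − (1 − pL)². A misdosed subject has probability M = 1 − (1 − pL)(1 − pH). The expected shift is (M − L)/12.
- pL 15%, pH 15%: 0
- pL 15%, pH 30%: (0.405 − 0.2775)/12 = 1.1 points
- pL 15%, pH 50%: (0.575 − 0.2775)/12 = 2.5 points
- pL 5%, pH 50%: (0.525 − 0.0975)/12 = 3.6 points

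**Would the higher dose be a better single column?** Take pL 15% and pH 50%. Without the misdosed subject the gap between columns is 0.750 − 0.2775 = 0.4725, or about 47 points.
- SAP rule: the lower column becomes (11 × 0.2775 + 0.575)/12 = 0.302, so the gap is 44.8 points.
- Higher-dose rule: the higher column becomes (12 × 0.750 + 0.575)/13 = 0.737, so the gap is 45.9 points.

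Both narrow the gradient. Only leaving the subject out of both single-dose columns keeps it unchanged.

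**The case against.** The strongest reply is that the plan already separates the doses where it matters. The primary reaction endpoints are defined after each immunization, and the unsolicited TEAE endpoint has separate prime and boost periods. For those tables the shift is zero. TEAEs with DLT are summarized for every interval and listed individually. Incorrect dosing is a candidate major deviation, and deviations and drug exposure are listed. SRC decisions rest on 48-hour data (Protocol 6.6.1), and no hypothesis is tested. All of this stands. A reader might infer that the rule distorts the main dose comparison or hides harm at the higher dose. The documents do not support that.

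A reader might also see a contradiction with SAP 5.1. It is only partial. A subject with two actual doses cannot be placed by an actual-dose rule alone, and the lower dose was one of those received. The difficulty is that a particular event after the higher dose is then filed under a dose that did not precede it most recently.

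A third inference is that the rule would absorb Cohorts 11 and 12 if they used unequal prime and boost doses. The sentence on combined analyses does not repeat the words about accident, and the protocol defines a cohort as "groups of subjects receiving the same vaccine dose and belonging to the same age group", so the wording is loose. But the paragraph opens with accidental dosing, and SAP 6.1.1 presents results by cohort, which would give a planned unequal regimen its own column. Table 2 marks only Cohorts 8 to 10 as already initiated, and the synopsis names only those as older-adult cohorts. Nothing shows that an unequal regimen was given.

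What the reply does not answer is the undefined term, the whole-regimen tables, and the late related TEAEs that have no boost-only table.

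**Conclusion.** The point holds in a limited form. For an accidental two-dose subject, outputs spanning both immunizations count events after the higher dose under the lower dose. The scope is unclear because combined analyses are not defined. The comparison by dose and immunization is sound.

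The size is small: at most 8.3 points in a 12-subject column for one misdosed subject, and 0 to 3.6 points in expectation under the assumed rates. The direction is to make the lower dose look worse and flatten the dose gradient in those tables. All of this is conditional on such a subject existing, which the documents do not show. Part A vaccinations were complete by 12 March 2021, before SAP version 3.0 of 27 April 2022, so the sponsor can establish this directly. The change is worth making because it is nearly free and removes an avoidable misattribution.

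**What to change.** Replace the sentence on combined analyses in SAP 6.1.1 with:

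> In tables spanning both immunizations, and in immunogenicity tables after boost, subjects who by accident received two different doses are shown in a separate prime/boost column (or footnoted and left out of the single-dose columns) and are kept in cohort-total. Any cohort planned with different prime and boost doses is reported as its own cohort.

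List the outputs covered: both reaction intervals together, TEAEs from prime to 28 days after boost, related TEAEs through Visit 10, and laboratory shifts to the worst value. Keep the existing display of each immunization under the dose given. Do not substitute a higher-dose rule, since that is not neutral either.

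The cost is one SAP paragraph and, if any such subject exists, one extra column or footnote. The downside is a slightly smaller n in the affected single-dose column, for example 11 instead of 12.

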6.1.2. Definitions and Derivations

Unscheduled visits

Unscheduled visits will not be included in the summary tables but will be included in the listings.

Variables

Baseline is defined as last value prior to first dose of IMP.

Change from baseline will be calculated as follows:

• Change from baseline = post-baseline assessment value – baseline assessment value

Duration [days] will be calculated as follows:

• Duration [days] = last observation date – first observation date + 1

Time from first immunization to first reaction will be calculated as follows:

Time from first immunization to first reaction [days] = first reaction date – prime immunization date + 1

Time from first reaction to last reaction will be calculated as follows:

Time from first to last reaction [days] = last reaction date – first reaction date + 1

Days since last immunization will be calculated as follows:

Days since last immunization = onset date of AE – date of last immunization + 1

For conversion of days to months or years the following rules will be applied:

• 1 month = 30.25 days

• 1 year = 365.25 days

Study Day and Treatment Day are defined as follows:

- · Study day:
- o If study date < date of first dosing, then study day = study date date of first dosing
- o If study date >= date of first dosing, then study day = study date date of first dosing + 1

Fold increase will be calculated as follows:

Fold increase = post-dose value / baseline value

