# 8.2.4 Clinical laboratory tests

See Section 10.2 for the list of clinical laboratory tests to be performed at the times given in the SoA (Section 1.3).

The investigator must review the laboratory report, document this review with signature and date, and record any clinically relevant changes occurring during the trial in the AE section of the CRF. The laboratory reports must be filed with the source documents.

All laboratory tests with values considered clinically significantly abnormal during participation in the trial should be repeated until the values return to normal or baseline or are no longer considered clinically significant by the investigator or the sponsor's Medical Monitor.

If such values do not return to normal/baseline within a period of time judged reasonable by the investigator, the etiology should be identified and the sponsor notified.

All protocol-required clinical laboratory tests (see Section 10.2) must be conducted in accordance with the trial site standard.

If laboratory values from non-protocol-specified laboratory assessments performed at the laboratory require a change in trial subject management or are considered clinically significant by the investigator (e.g., SAE, AE or dose modification), then the results must be recorded in the CRF.

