#### Fever

Fever is defined as an oral temperature of ≥38.0°C. Temperature will be measured and recorded to 1 decimal place and then categorized during analysis according to the scale shown in Table 6.

Table 6: Fever grading scale

	Mild (Grade 1)	Moderate (Grade 2)	Severe (Grade 3)	Potentially life-threatening (Grade 4)
Fever	38.0-38.4°C	38.5-38.9°C	39.0-40.0°C	>40.0°C

If a fever of ≥39.0°C is recorded by a subject during the 7-day post-vaccination diary period, a telephone contact should occur to ascertain further details and determine whether a site visit is clinically indicated. Only an investigator or medically qualified person is able to confirm a participant's fever as >40.0°C for recording the trial database. If a participant experiences a confirmed fever >40.0°C, the investigator must immediately notify the sponsor and, if it is determined to be related to the administration of the study intervention, further vaccinations will be discontinued in that participant.

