6.4. Primary Analyses

Hereinafter, the primary analyses for Part A are described.

The primary endpoints are solicited local reactions at the injection site, solicited systemic reactions and the proportion of subjects with at least 1 unsolicited treatment emergent adverse event (TEAE).

Clarification: Only local and systemic reactions assessed by subject will be analysed as primary endpoint. As additional analyses, the local and systemic reactions assessed by the investigator will also be included in tables displaying "worst possible grade" for data completeness.

All primary analyses will be performed using the SAF and analyses of adverse events will possibly be repeated using the SAFB.

All primary analysis endpoints will be summarized by group (i.e. by cohort) and all cohorts combined (cohort-total).

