6.7.2. Laboratory Assessments

Definition

Clinical laboratory data to be summarized includes hematology, clinical chemistry, and urinalysis and will be assessed at the time-points indicated in Table 3 of the protocol.

The following clinical laboratory variables will be assessed:

Hematology

Hemoglobin, hematocrit, red blood cell count, white blood cell count and differential (neutrophils, lymphocytes, monocytes, eosinophils, basophils), platelet count.

Clinical chemistry

Alkaline phosphatase, creatinine, ferritin, C-reactive protein, albumin, alanine aminotransferase, amylase, aspartate aminotransferase, gamma glutamyl transpeptidase, total bilirubin, blood urea nitrogen, glucose, lipase, sodium, potassium, calcium.

Follicle-stimulating hormone: Only in women who are not of childbearing potential.

Urinalysis

Dipstick: glucose, bilirubin, ketone, specific gravity (1 mL \triangleq 1 g), blood, pH, protein, urobilinogen, nitrite, and leukocytes.

Microscopic urinalysis: If warranted by dipstick results, urine sediment will be microscopically examined for presence of red blood cells, white blood cells, casts, crystals, epithelial cells, and bacteria.

All laboratory tests are classified as normal or lower or higher than reference range (abnormal). All abnormal laboratory tests will be classified by the investigator as clinically significant (CS) or not (NCS).

Abnormal lymphocytes data will be categorized as defined in table 9 in the protocol as grade 1 (mild), grade 2 (moderate), grade 3 (severe) and grade 4 (potentially life threatening).

Analysis

Clinical laboratory variables at each time-point and its change from baseline to each post-baseline time-point (for continuous variables) will be summarized using descriptive summary statistics for each parameter by group and cohort-total.

Number and percentage of subjects with low, normal and high clinical laboratory values at each time-point will be summarized for each parameter by group and cohort-total. The same table will be provided for the grading scheme (grades mild, moderate, severe and life threatening) for lymphocytes.

The number and percentage of subjects with CS abnormal, abnormal (not CS), normal and missing values will be summarized for each parameter by group and cohort-total.

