Clinical laboratory values for each parameter will be summarized using shift tables from baseline to worst post-baseline value with respect to reference range values (low, normal, high) by group. Worst post-baseline might be in both directions. Each subject may be counted in the parameter high and in the parameter low category. A subject will only be counted in the normal category if

all post-baseline values are normal. If several post-baseline values are considered as worst post-baseline value, the first one is taken.

All clinical laboratory data will be presented in the data listings along with normal ranges. Abnormal clinical laboratory values will be flagged in the listing.

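### The exclusion of unscheduled visits should not reach the worst-value laboratory tables, the abnormality counts not given by visit, or the investigator worst-grade tables

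*SAP*

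**What the plan says.** Two general rules govern the tables. SAP 6.1.2: "Unscheduled visits will not be included in the summary tables but will be included in the listings". SAP 6.1.1: "Descriptive summary tables as well as figures will be based on scheduled visits". No exception appears in these sections or in the sections on individual outputs.

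Three kinds of output are not simple by-visit summaries:

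- **Laboratory shift table (SAP 6.7.2).** "Clinical laboratory values for each parameter will be summarized using shift tables from baseline to worst post-baseline value with respect to reference range values", in the categories low, normal and high. A subject is placed in the normal category only when every post-baseline value is normal.
- **Clinically significant, abnormal, normal and missing counts (SAP 6.7.2 and 6.7.3).** These are given per parameter and cohort for laboratory tests and vital signs, without saying whether they are by visit.
- **Investigator worst-grade tables (SAP 6.4 and 6.4.1).** As additional analyses, "the local and systemic reactions assessed by the investigator will also be included in tables displaying" the worst possible grade, alone and combined with the diary.

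The protocol foresees assessments outside the schedule. Section 8.2.4: "All laboratory tests with values considered clinically significantly abnormal during participation in the trial should be repeated until the values return to normal". Section 8.10 allows extra blood samples for safety after adverse events. Sections 8.2.11 and 8.2.12 allow ad hoc site visits after a hotline report or wellbeing call. For a diary temperature of 39.0°C or more, section 10.3.1.11 says "a telephone contact should occur to ascertain further details and determine whether a site visit is clinically indicated".

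**The concern.** Restricting by-visit means and counts to scheduled visits is ordinary practice, because it keeps extra measurements in unwell subjects from distorting a time point. A worst-value table has the opposite purpose: it should pick up the most extreme result whenever it was seen. Unscheduled visits in this trial arise mostly because something looked wrong, so the records left out are not a random subset.

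SAP 6.7.2 also sits badly with the general rule. It asks that all post-baseline values be normal before a subject counts as normal, while 6.1.1 and 6.1.2 remove some of those values. Two programmers could reasonably build different tables. At stake is whether the supporting safety tables of a small safety trial show an abnormality that was in fact observed.

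**Working it through.** **Step 1. Which tables can the rule reach?**

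| Output | Built from | Reached by the rule? |
|---|---|---|
| Solicited reactions, primary endpoint (SAP 6.4) | Subject's daily diary | No |
| TEAEs, including worst grade (SAP 6.4.3) | AE records, placed by onset date and time | No |
| By-visit laboratory and vital-sign summaries | Visits | Yes, and rightly |
| Lymphocyte grades (SAP 6.7.2) | Visits, by time point | Yes, and rightly |
| Laboratory shift to worst post-baseline value | Visits | Yes |
| Clinically significant/abnormal counts, where not by visit | Visits | Yes |
| Investigator-assessed and combined worst grade | Visits, plus the diary for the combined table | Yes, for the investigator part |

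The lymphocyte row follows from SAP 6.7.2: "The same table will be provided for the grading scheme (grades mild, moderate, severe and life threatening) for lymphocytes", where the table meant is the one at each time point.

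**Step 2. Which off-schedule findings would change the affected tables?**

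- Scheduled value high, repeat higher: still high in a low/normal/high table. No change.
- All scheduled values normal, first abnormal value off-schedule: shown as normal if 6.1.2 is applied as written.
- Scheduled value low, off-schedule value high: the high entry is missing, although SAP 6.7.2 lets one subject count in both directions.
- Investigator grades a reaction higher at an ad hoc visit than at any scheduled visit: the investigator table shows the lower grade, and so does the combined table unless the diary holds the higher one.

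So the exposure is to an abnormality, a direction or an investigator grade *first* seen off-schedule.

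**Step 3. Direction.** Scheduled records are a subset of all records. The worst value over a subset cannot be worse than over the whole set, so the exclusion can only lower an abnormal count or leave it unchanged.

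**Step 4. Where the schedule leaves room.** Protocol Table 3 has post-dose laboratory draws at Visits 2, 3, 5 and 7 (Days 2, 8, 29 and 50). After the boost on Day 22, on-site reaction assessments are at 1, 3 and 6 h and next at Visit 5, which is also the next laboratory draw. Visit 5 is Day 29±3, so Day 26 at the earliest, and 26 − 22 = 4. From 6 h until about day 4 after boost at the earliest, and day 7 nominally, nothing of this kind is scheduled on site. The 48 h call for the first six subjects is questioning, not examination.

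**Step 5. Size.** The plan's own figure first (Protocol 9.2, SAP 4): 1 − 0.85^12 = 0.8578, against the stated 85.8%. It reproduces, and the rule does not alter it, because TEAEs are not collected by visit.

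One subject in a cohort of 12 is 1/12 = 8.3 percentage points. Exact 95% limits are 0 to 26.5% for 0/12 and 0.2 to 38.5% for 1/12.

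For illustration only, suppose a laboratory finding has 15% incidence and a share u of such findings is seen only off-schedule. Neither assumption comes from the documents. The chance that the table shows at least one case is 1 − (1 − 0.15(1 − u))^12:

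| u | Chance |
|---|---|
| 0 | 85.8% |
| 10% | 82.5% |
| 25% | 76.1% |
| 50% | 60.8% |

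**The case against.** The strongest reply is that the outputs carrying the primary objective are untouched, and this stands. A reader might infer that severe reactions are dropped from the primary endpoint. They are not. The fever that prompts a possible site visit is already in the diary, and an adverse event first reported at an ad hoc visit still enters by its onset date. The investigator tables are supplementary.

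The reply also holds on several other points:

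- Most repeat tests follow a value already out of range, so they do not move a subject in a low/normal/high table.
- Nothing is deleted. Unscheduled values are listed and abnormal ones flagged, and listings for 12 subjects can be read one by one.
- A reader might take everything measured on days 1 to 6 after boost to be unscheduled. The Visit 5 window rules that out, since a scheduled visit may fall on days 4 to 6.

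Clinically significant findings also have a second route. Protocol 8.2.4 and 10.3.1.7 send them to the AE record. That cover is partial. Under 10.3.1.9 only the diagnosis or symptoms are recorded where these exist, not the laboratory or vital-sign value. Under 10.3.1.1 reactogenicity need be an AE only if it adds clinically significant information not available elsewhere.

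The reply does not remove the conflict inside the SAP. A table labelled worst post-baseline that omits some post-baseline values does not show what its label says.

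**Conclusion.** The concern holds in a limited form and should be corrected. Applied as written, SAP 6.1.1 and 6.1.2 can make the laboratory worst-value shift table, the abnormality counts not given by visit, and the investigator part of the worst-grade tables miss findings first seen off-schedule. The possible error runs one way, at 8.3 percentage points per subject in a cohort of 12.

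This rests on two readings: that the general rule overrides the requirement in SAP 6.7.2 that all post-baseline values be normal, which the SAP does not settle, and that the clinically significant/abnormal counts are not by visit. Protocol 9.4.5 plans those laboratory counts by parameter and visit. If that is how they are built, the exclusion is appropriate for them.

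It would go too far to conclude that severity in this trial is understated. The documents do not show how many worst values came from unscheduled visits, and the number could be zero.

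**What to change.** Amend SAP 6.1.1 and 6.1.2 so that the exclusion applies only to by-visit descriptive summaries and their figures. Add that three outputs use all post-dose assessments, scheduled and unscheduled, within the stated interval: the worst post-baseline shift tables, any clinically significant abnormality count not presented by visit, and the investigator-assessed and combined worst-grade reaction tables. State in 6.7.2 and 6.7.3 whether the clinically significant/abnormal counts are by visit.

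The cost is a short SAP edit and a changed record filter in a few programs, with no new data. Any of these tables already produced would need a rerun. The downside is that some abnormal counts may become slightly less favourable.
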